9.0 Data Management

9.1. Data Collection Table

9.1.1. Aim 1

a) APP

	Eligibility and consent form	Baseline Assessment	Post-Interview Assessment
Informed Consent	X		
Demographics		X	
Focus Group Interview		X	

9.1.2. Aim 2

a) APP/Hematology/Oncology Fellow

	Eligibility and consent form	Baseline Assessment	Post-Intervention Assessment
Informed Consent	X		
Demographics		X	
Qualitative Interview			X (at the end of the study)
Clinician Acceptability Questionnaire			X
Clinician Confidence Questionnaire		X (before and after SICP training)	X (at the end of the study)

b) Patient

Version Date: 5/10/23

PRMC#: UOCPC22039

Study Protocol

ClickIRB #: STUDY00007403

	Eligibility and consent form	Baseline Assessment	Post-Intervention Assessment
Informed Consent	X		
Demographics		X	
Clinical and Cancer Characteristics		X	
Cancer Health Literacy (CHLT-6)		X	
Disease Understanding		X	X
Activities of Daily Living (ADL), Instrumental Activities of Daily Living (IADL), Fall History		X	
Nutritional Status		X	
Geriatric Depression Scale-15		X	
Mini-Cog		X	
ACP Engagement Survey		X	X
Qualitative Interview			X
Patient Acceptability Questionnaire			X
End-of-Life Quality Indicators			X (up to 5 years or death; EMR)

c) Caregiver (if applicable)

	Eligibility and consent form	Baseline Assessment	Post-Intervention Assessment
Informed Consent	X		
Demographics		X	
Qualitative Interview			X
Acceptability Questionnaire			X

9.2. All hardcopy research records will be stored onsite in the URMC, in locked research files at the Wilmot Cancer Institute (WCI). The Cancer Center is secured with electronic key cards. Offices within the Cancer Center are again secured by key and data is kept in locked file cabinets. Electronic research records are stored on the URMC's password secured and firewall

Version Date: 5/10/23

PRMC#: UOCPC22039

Study Protocol

ClickIRB #: STUDY00007403

protected networks. These are the same methods of security used for patient medical records. For audio-recordings, these will be uploaded to Box within a week of the interview and deleted from the audio recorder. All study data will be kept for a period of 7 years after the study and all reports and publications are complete.

9.3. All data collected for the current study will be used in post hoc analyses as appropriate. Data will not be used for future studies without prior consent of the patient. The patient's individual research record will not be shared with their treating physician, unless they provide consent or the patient's treating physician is a study physician, in which case they will have access to study data as a study co-investigator. Overall study results will be presented to participants, faculty and staff at the URMC after completion of the study. Study results will be presented at professional meetings and published.

9.4. The study coordinator will assign a numerical study ID to each participant once they have signed the consent form (chronologically based on the data they signed consent i.e., 001, 002, 003...). All study forms and questionnaires will use this number and the participant's first, middle, and last initials as identifiers, to ensure data integrity. Other identifying information will not exist on these forms. A complete list of study participants with study ID, name, and contact information will be maintained separately. This linkage information will only be accessible to the study coordinator, study investigators, and the individuals responsible for maintaining the database.

9.5. Additionally, data on the socio-demographics, clinical, and cancer and treatment characteristics will be collected and managed by the research teams at URMC using REDCap electronic data capture tools hosted at URMC.³² We will also evaluate the medical records for clinical characteristics and outcomes, and utilize REDCap to collect and manage this information.

9.5.a. URMC provides the following information on the REDCap program: "Vanderbilt University, in collaboration with a consortium of institutional partners, has developed a software toolset and workflow methodology for electronic collection and management of research and clinical trial data, called REDCap (Research Electronic Data Capture). The REDCap system is a secure, web-based application that is flexible enough to be used for a variety of types of research. It provides an intuitive interface for users to enter data and real time validation rules (with automated data type and range checks) at the time of data entry. REDCap offers easy data manipulation with audit trails and functionality for reporting, monitoring and querying patient records, as well as an automated export mechanism to common statistical packages (SPSS, SAS, Stata, R/S-Plus). Through the REDCap Consortium, Vanderbilt has disseminated REDCap for use around the world. Currently, over 240 academic and non-profit consortium partners on six continents with over 26,000 research end-users use REDCap.³³

9.5.b. According to the Clinical and Translational Science Institute (CTSI), REDCap is

supported with the following means. “The *CTSI Informatics Core*, a unit of the SMD *Academic Information Technology (AIT) Group*, will serve as a central facilitator for data processing and management. REDCap data collection projects rely on a thorough study-specific data dictionary defined in an iterative self-documenting process by all members of the research team, with planning assistance from the *AIT-CTSI Informatics Core*. The iterative development and testing process results in a well-planned data collection strategy for individual studies.³¹

9.5.c. The CTSI states that regarding security, “REDCap servers are housed in a local data center at the University of Rochester and all web-based information transmission is encrypted. REDCap was developed in a manner consistent with HIPAA security requirements and is recommended to University of Rochester researchers by the URMC Research Privacy Officer and Office for Human Subject Protection.³³

10.0 Risks/Benefit

10.1. Risks

There is potential loss of confidentiality associated with participation in the proposed study. In terms of loss of confidentiality, quantitative data from participants will need to be stored. Though rigorous and well-tested data safety and security guidelines will be observed, there is still a chance that confidentiality could be breached, and sensitive medical information could become known to persons outside the research team.

Advarra will be used as the direct payment system for study payments. During registration or account creation on the site, Advarra may collect any or all of the following subject information, (i) name, (ii) home or business address, (iii) professional information, including specialty or nature of concern, (iv) organization with whom they are affiliated and its address, and (v) email address. When they visit the site using their personal smart device, the site may automatically record information that their browser sends like, the name of the domain and host from which they access the Internet; the Internet Protocol (IP) address of the computer or smart device they are using; the date and time they access the site or make uploads or post to the site; and the Internet address of the website from which they linked directly to the site. This information does not include any Personally Identifiable Information and we refer to this information as non-identifiable information.

There is still a risk that a third party could gain access to any Information provided to or collected through this site. To mitigate these risks, any data breaches and, potential identification of the subjects, Advarra has security measures in place to protect electronically transmitted information. They are frequently reviewing and consistently trying to improve the security of the site. They do not collect and subjects will not be asked to submit any “protected health information” as defined in HIPAA.

10.2. Benefits

There are no anticipated benefits to the participants.

10.3 Payments and Costs

Patients and caregivers participating will be paid \$10 for their participation in the form of gift cards following their inpatient APP/hematology/oncology fellow-delivered ACP visit. APPs/hematology/oncology fellows will not be reimbursed for their participation. However, for APPs, if we have to schedule the training on how to deliver the ACP intervention outside of the APP working hours, they will be paid for those working hours by the APP leadership (confirmation with APP leadership through email communication). There are no additional costs to patients and caregivers for participating in this study.

Version Date: 5/10/23

PRMC#: UOCPC22039

Study Protocol

ClickIRB #: STUDY00007403

For this study we will use a subject payment system called Advarra Participant Payments. The system allows three ways to provide payment. Subjects can choose: a reloadable debit card; direct deposit; or mailed paper checks. The study team will help create a “subject profile” in the system. In order to provide payment, the subject will need to enter their name and date of birth into their subject profile. Depending on which payment method they choose, they may also need to enter their email address and banking information. If the subject already has an Advarra account (because of another study that uses this system), the existing profile will be used to provide payment.

10.4 Future Work

Results of this study can be expanded to guide ACP interventions for other types of cancers. It can also be translated to other languages.

Version Date: 5/10/23
PRMC#: UOCPC22039
Study Protocol
ClickIRB #: STUDY00007403

11.0. DATA SAFETY AND MONITORING

Only adverse events (AEs) related to the study intervention or procedures will be reported. In other words, AEs related to cancer treatment will not be reported.

11.1. Adverse Event Reporting Requirements

11.1.1. Adverse events will be reported using the URCC Adverse Event form and/or as required by the Cancer Center Clinical Trials Office.

	Grade 1	Grade 2			Grade 3				Grade 4		Grade 5	
		Unexpected		Expected	Unexpected		Expected		Unexpected	Expected	Unexpected	Expected
		with hospitalization	without hospitalization		with hospitalization	without hospitalization	with hospitalization	without hospitalization				
Unrelated	Not Required	Not Required	Not Required	Not Required	Not Required	Not Required	Not Required	Not Required	10 Calendar Days	Not Required	10 Calendar Days	10 Calendar Days
Unlikely	Not Required	Not Required	Not Required	Not Required	Not Required	Not Required	Not Required	Not Required	5 Calendar Days	10 Calendar Days	5 Calendar Days	10 Calendar Days
Possible	Not Required	10 Calendar Days	Not Required	Not Required	10 Calendar Days	10 Calendar Days	Not Required	Not Required	24-Hour; 5 Calendar Days	10 Calendar Days	24-Hour; 5 Calendar Days	10 Calendar Days
Probable	Not Required	10 Calendar Days	Not Required	Not Required	10 Calendar Days	10 Calendar Days	Not Required	Not Required	24-Hour; 5 Calendar Days	10 Calendar Days	24-Hour; 5 Calendar Days	10 Calendar Days
Definite	Not Required	10 Calendar Days	Not Required	Not Required	10 Calendar Days	10 Calendar Days	Not Required	Not Required	24-Hour; 5 Calendar Days	10 Calendar Days	24-Hour; 5 Calendar Days	10 Calendar Days

Hospitalization is defined as initial hospitalization or prolongation of hospitalization for ≥ 24 hours, due to adverse event.

11.1.2. Adverse events will be reported in accordance with the following guidelines:

11.1.3. Adverse event reports will be submitted in one of the following ways:

- (1) By email: (pdf)
- (2) By mail:
- (3) By fax:

11.1.4. An unexpected adverse event is defined as any adverse experience, the specificity or severity of which is not consistent with the risk information. This is a minimal risk study as both exercise and mobile app-driven interventions have been shown to improve outcomes in community-dwelling older adults. If study bone marrow biopsy is collected, this would be a greater than minimal risk study.

11.1.5. A serious event refers to any event in which the outcome results in any of the following: death, a life-threatening adverse experience, inpatient hospitalization or prolongation of existing hospitalization, a persistent or significant disability, incapacity, or a congenital anomaly/birth defect. Important medical events that may not result in death, be life-threatening, or require hospitalization may be considered a serious adverse drug experience when, based upon appropriate medical judgment, they may jeopardize the participant and may require medical or surgical intervention to prevent one of the outcomes listed in this definition. We anticipate that any serious events will be related to standard of care cancer treatments and not due to the intervention. We will not collect adverse events related to cancer treatments.

11.1.6. Adverse events will be reported in accordance with institutional policies (University of Rochester, Research Subject Review Board, local IRB, URCC CCOP, CTO, and DSMB) as per their requirements.

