During the ACP visit, the APP/hematology/oncology fellow will discuss ACP and EOL care. This visit will be recorded. After the visit, the study subject and caregiver (if applicable) will complete post-intervention measures. Within 4 weeks of the in-patient visit, we will conduct an interview with the patient and caregiver (if applicable) either in-person or via zoom/phone for 30-60 minutes. We will also conduct an interview with the APPs/hematology/oncology fellows who participated in the ACP visits with the patients at the end of the study. All parties present for the recorded visit, including enrolled patients, any accompanying caregivers, family or friends, the APP/hematology/oncology fellow, and any other physicians or health care providers not participating in the study will be fully aware that the conversation is being audio- recorded before any recording begins, in addition to the prior written consent of enrolled patients. Patients, caregivers, and APPs/hematology/oncology fellows may request access to the audio recording or the written transcript.

In order to collect data from the EMR regarding EOL metrics, patients in this study will be followed until death or up to 5 years following their participation.

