11.2. Data Safety Monitoring

11.2.1. All adverse events requiring reporting will be submitted to the current Project Coordinator as described in Section 11.1. Serious adverse event reports will be forwarded to the study chair and the Data Safety and Monitoring Committee (DSMC). Adverse events are entered into a protocol-specific spreadsheet.

11.2.2. Adverse event rates are monitored utilizing the spreadsheet. If a serious adverse event is reported frequently, the study chair will conduct a detailed review. The DSMC Committee Chair will be notified and will determine if further action is required.

11.2.3. The Data Safety Monitoring Committee (DSMC) will review study progress and cumulative reports of adverse events every year and as needed. An overall assessment of accrual and adverse events will enable the committee members to assess whether significant benefits or risks are occurring that would warrant study closure.

References:

2. SEER Cancer Statistics Factsheets: Acute Myeloid Leukemia. National Cancer Institute. Bethesda M, <http://seer.cancer.gov/statfacts/html/amyl.html>.
7. Mederios BC S-HS, Momin F, Parisi M. Real-World Treatment Patterns and Comparative Effectiveness Among a Population of Elderly Patients with Acute Myeloid Leukemia (AML). 132(Supp 1):835

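### Section 11.1.4 names no reference for expectedness and argues minimal risk from interventions this study does not give, and the 11.1.1 table leaves some related events unreported that 11.1.5 calls serious

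*Combined protocol and SAP*

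**What the plan says.** Section 11.0 confines reporting to events related to the intervention or the study procedures. Within that scope, these places bear on the point:

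- **11.1.4** defines expectedness: "An unexpected adverse event is defined as any adverse experience, the specificity or severity of which is not consistent with the risk information". It does not say which section or document holds that information. It continues "This is a minimal risk study as both exercise and mobile app-driven interventions have been shown to improve outcomes in community-dwelling older adults", and then "If study bone marrow biopsy is collected, this would be a greater than minimal risk study".
- **10.1**, the protocol's own section on risks, opens with "There is potential loss of confidentiality associated with participation in the proposed study" and adds the risk that outsiders reach data held in the payment system. It lists no clinical or psychological risk.
- **11.1.1** gives a table of reporting times by causality, grade and expectedness, and in some columns by hospitalization. Its footnote reads "Hospitalization is defined as initial hospitalization or prolongation of hospitalization for ≥ 24 hours, due to adverse event".
- **11.1.5** lists what makes an event serious, including "inpatient hospitalization or prolongation of existing hospitalization".
- **11.2.1** says "Serious adverse event reports will be forwarded to the study chair and the Data Safety and Monitoring Committee (DSMC"). The same item submits to the project coordinator those events that 11.1 requires to be reported.

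The intervention is a conversation (7.1): "During the ACP visit, the APP/hematology/oncology fellow will discuss ACP and EOL care". Patients must be inpatients to enter (3.5), and the visit takes place during the same admission (4.3, 7.1).

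**The concern.** There are two separate faults.

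The first is in 11.1.4. A reader who wants to classify an event as expected or unexpected finds a definition that points to an unlocated source. It is followed by two sentences about exercise, a mobile app and a bone marrow biopsy. None of these appears in the study outline, the list of measures or the data collection tables, and the population is in hospital, not in the community. The sentences cannot support the risk label they are there to support.

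The second is that the table and the definition of serious do not fit together. The table can require no report of a related event that 11.1.5 calls serious. The DSMC reviews cumulative adverse event reports every year and as needed, and considers closure on that basis (11.2.3). A related serious event with no required report could be missing from what it sees. Because every patient is already in hospital at entry, prolongation of the stay is a criterion that can apply to any of them.

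**Working it through.** The plan states no figure here, and no sample size or rate enters. The check is to read the table cell by cell and set it against 11.1.5.

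**Step 1. Is the table legible?** The header gives 1 column for Grade 1, 3 for Grade 2, 4 for Grade 3, 2 for Grade 4 and 2 for Grade 5: 1 + 3 + 4 + 2 + 2 = 12. Each of the five causality rows has 12 entries, so the cells map to the columns without guessing.

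**Step 2. What do the rows for related events require?** The Possible, Probable and Definite rows are identical:

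| Event | Unexpected | Expected |
|---|---|---|
| Grade 1 (one column) | no report | no report |
| Grade 2 with hospitalization | 10 days | no report (column not split) |
| Grade 2 without hospitalization | no report | no report (column not split) |
| Grade 3 with hospitalization | 10 days | no report |
| Grade 3 without hospitalization | 10 days | no report |
| Grade 4 | 24 hours; 5 days | 10 days |
| Grade 5 | 24 hours; 5 days | 10 days |

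Expectedness therefore decides whether a report is made in three situations: Grade 2 with hospitalization, and Grade 3 with and without it. At Grades 4 and 5 it changes only the timing.

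**Step 3. Set this against 11.1.5.** The hospitalization criterion there carries no condition on grade, expectedness or length of prolongation. Three kinds of related event meet it and still need no report under the table:

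- (a) Grade 3, expected, with hospitalization.
- (b) Grade 2, expected, with hospitalization.
- (c) Grade 2, unexpected, prolonging the stay by less than 24 hours. The footnote's threshold moves it to the column without hospitalization.

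Each occurs in 3 of 3 related rows. The 24-hour threshold has no effect at Grade 3: comparing with and without hospitalization over 5 rows and 2 expectedness classes gives 10 pairs, all identical.

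**Step 4. How does the answer depend on the reference for expectedness?**

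- If the reference is 10.1, a clinical event such as severe distress after the visit is not consistent with the listed confidentiality and payment-data risks. It is unexpected, and is reported in 10 days at Grade 3, or at Grade 2 with hospitalization as the footnote defines it. Gaps (a) and (b) are then latent, because no clinical event reaches those cells.
- If the reference is some other list or the investigator's judgement, a foreseeable event may be called expected, and (a) and (b) open.
- Gap (c) concerns unexpected events, so it remains when 10.1 is the reference.

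**The case against.** The strongest reply is that little harm follows in practice. The foreign sentences in 11.1.4 explain a risk label and list no expected events, so nobody could classify an event against them. Under 10.1 a clinical event is unexpected and the worst cells are never reached. Section 11.1.1 adds whatever the Clinical Trials Office requires, and 11.1.6 adds institutional, IRB and DSMB requirements. Section 11.2.1 also has adverse events entered in a spreadsheet, with no stated limit to reportable events, and 11.2.2 monitors rates from it. Section 11.1.5 anticipates that any serious events will come from cancer treatment.

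Most of this stands, and it limits the point. It does not remove it. The protocol does not say that 10.1 is the reference, the content of the outside policies is not given, and gap (c) does not depend on expectedness.

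A reader might infer more than the documents support:

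- *That the exercise and app text decides expectedness.* It does not; the reference is simply unnamed. Nor can it be said that no reference exists, since consent pages were removed from the text reviewed. That the sentences were carried over from another protocol is a fair guess, but is not stated.
- *That one and the same event is reported in 10 days or never.* Under 10.1 a Grade 3 event is reported, and the policies and spreadsheet may catch others.
- *That the waiver of documented consent in 4.1.4 loses its basis.* That waiver covers clinicians and caregivers, gives its own grounds and does not cite 11.1.4. Patients sign a consent form.

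**Conclusion.** The point holds as an inconsistency in the written safety rules. Section 11.1.4 leaves the expectedness reference unnamed and supports minimal risk with interventions that are not in this study. In all three rows for related events, the table requires no report of expected Grade 2 and Grade 3 events with hospitalization, or of unexpected Grade 2 events with prolongation under 24 hours, although 11.1.5 makes them serious.

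The size is modest. Related Grade 4 and 5 events are always reported. The gap for expected events is latent if 10.1 is the reference. The documents give no rate for serious events caused by the visit, so the number of reports affected cannot be estimated. No feasibility or efficacy result changes. What is at stake is the completeness of what the study chair and the DSMC receive.

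This rests on two assumptions: that 11.1.5 is meant to apply as written, with no minimum length of prolongation, and that the outside policies, which could not be seen, do not already close the gaps.

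**What to change.** Amend the wording in three places.

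1. In 11.1.4, replace the exercise, app and biopsy sentences with a rationale for the ACP visit, and name 10.1 as the reference for expectedness.
2. Below the 11.1.1 table, state that any event that meets 11.1.5 and is judged at least possibly related to the study visit or procedures is reported, and is forwarded to the study chair and the DSMC, whatever its grade or expectedness. State the time limit with it.
3. Use one definition of hospitalization in the table footnote and in 11.1.5.

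Items 1 and 2 belong together. If 10.1 is later extended to list clinical or psychological effects of the conversation, those effects become expected, and without item 2 the latent gap at Grades 2 and 3 would open.

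The cost is a protocol wording amendment and possibly a few more reports. No extra patients, visits or procedures are needed.
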